#### **4.8.1.1 Non-attendance of Follow-up Assessments**

Attempts should be made to contact subjects discharged from hospital who do not attend their study follow-up assessments to ensure their well-being. In such cases, the subject will be contacted at least twice by telephone and once by letter to request that they attend the scheduled follow-up assessment. If subjects do not respond they will be considered as withdrawn at that time point (lost to follow-up). If a subject is lost to follow-up, wherever possible mortality data will be sought at all remaining mortality time points from alternative sources such as the subject's local physician or health records.

#### **4.8.2 Replacement Policy**

A screen failure subject is defined as any subject who did not comply with the inclusion and exclusion criteria during screening **and** prior to receiving the first dose of study drug. Subjects who become ineligible after consenting, and before treatment, will be deemed to be screen failures and will be replaced.

Subjects who complete screening and are randomized and receive the first dose of study drug will not be replaced even if later withdrawn or lost to follow-up.

It is possible that a subject may be randomized to a study group following successful screening but may become ineligible prior to administration of the first dose of study drug. For example, prior to the first dose of study drug a subject may deteriorate and require mechanical ventilation. Such subjects will be classed as screen failures and will be replaced.

Subject numbers (and randomization numbers if applicable) of screen failures will not be reallocated. A new subject will be enrolled and assigned the next available number.

### **4.9 Planned Sample Size and Number of Study Centres**

It is planned to randomise and dose 140 subjects at approximately 5-15 centres in the USA and possibly also in other countries. See [Section 7.4](#) for a discussion of sample size.

### **4.10 Subject Identification and Randomization**

#### **4.10.1 Subject Identification**

A unique subject number (subject identification number) will be allocated to study patients. The subject number will be assigned at the study centre on enrolment (i.e., provision of written informed consent) in chronological order of screening and will be used throughout the study. If a subject is not subsequently randomized, their screening number will not be reallocated. Each screened subject will therefore have a unique identifier.

#### **4.10.2 Randomisation Scheme**

Subjects will be randomized on a 1:1 basis to FP-1201-lyo or dexamethasone. IWRS will be used to obtain randomisation details.

To ensure that conclusions are not dominated by data from a small number of centres, and also to obtain a broad spread of subjects and centres within the constraints of the inclusion/exclusion criteria, each centre will be allowed to include up to, but no more than, 30 patients.

FP-1201-lyo 10 µg powder for solution for injection  
(lyophilized human interferon beta-1a)

page 33 (60)

Randomisation will be stratified by gender and age (under 70 years and 70 years and older). A sequence of randomisation numbers will be assigned to each study centre.

Refer to [Section 5.4](#) for details of blinding and breaking the blind.

#### **4.10.3 Randomisation of Subjects to Treatment**

Randomisation of patients to treatment will occur during screening or on D1 after all screening procedures have been performed and eligibility for inclusion in the study has been confirmed. Each randomized subject will receive a unique randomisation number. Randomized subjects who terminate their study participation for any reason, regardless of whether study drug was taken or not, will retain their randomisation number.

The Investigator will use IWRS for randomisation of study subjects, details can be found in the study file.

#### **4.11 Minorities and Women**

No patients will be excluded on the basis of race, ethnicity, or sex. The Steering Committee and the Sponsor will monitor recruitment of minorities and women, and this recruitment will also be reviewed by the IDMC.

### **5 STUDY DRUG**

#### **5.1 Identity**

Pharmacy manual contains the relevant information on the study IMP manufacturers, packagers and distributors.

#### **5.2 Packaging, Labelling and Storage**

FP-1201-lyo is provided by Faron to clinical sites. Dexamethasone (commercially available) and 0.9% Saline solution will be sourced locally by the sites.

FP-1201-lyo is secondary packaged in a carton, containing one vial. The dexamethasone packaging configuration may vary based on the source chosen by the clinical site.

Six investigational medicinal kits are provided per patient. These are reserved for each patient to cover the 6-day treatment period.

Labelling will be prepared to meet the local regulatory requirements.

All study drug supplies must be stored in accordance with the manufacturer's instructions, e.g., FP-1201-lyo kits are to be stored at 2–8°C (35.6°F–46.4°F) until dispensed to the patients. The study drug is to be stored in a securely locked area, accessible to authorised personnel only. The IMPs are dispensed and prepared only after approval by the Investigator or by a member of staff specifically authorised by the Investigator, or by a pharmacist, as appropriate.

#### **5.3 Administration**

Study IMP FP-1201-lyo (IFN beta-1a) 10 µg or dexamethasone 6 mg will be prepared for clinical application according to the instructions provided in the Pharmacy Manual. The IMP will be prepared by an unblinded site staff (i.e. Pharmacist) according to the randomization code and dispensed into a blinded syringe. The prepared IMPs will be administered as two intravenous bolus injections via a central or peripheral line. To maintain blinding at administration, every study subject will receive two separate bolus injections of IMP (either IFN-beta -1a/Saline, and another injection of

Saline/Dexamethasone). The exact time of both injections will be recorded and the injections will be followed with a 5 mL flush of sterile saline (not provided). Administration should be performed by blinded site personnel.

IMP injections will be given once daily for 6 days, unless the patient is discharged from the hospital. The injections should be given at the same time each day  $\pm$ 1 hour providing the patient's condition allows this. If for any reason this is not possible, the treatment should be given as soon as possible. The reason for the delay must be entered in the e-CRF. Subsequent doses should not be delayed and should revert to the original time schedule (e.g., if the D1 dose was at 13:00, the D2 dose was delayed and given at 17:00, the D3 dose should be given at 13:00  $\pm$ 1 hour). No dose modifications or temporary cessations of IMP administration are allowed. If a delay is more than 12 hours, the patient must discontinue from study IMP, but all data must continue to be collected per protocol. Administration of a second 6-day course of study IMP is not permitted.

#### **5.4 Blinding and Breaking the Blind**

The study will be performed in a double-blind and randomized manner. IMP (IFN beta-1a and dexamethasone) will be prepared in identical syringes by an unblinded person, thereby enabling fully blinded conditions.

The treating physician is responsible for the medical care of the trial patient and the study set up allows the investigator/treating physician to rapidly break the treatment code in an emergency situation.

The study blind should only be broken in a medical emergency (where knowledge of the study drug received would affect the treatment of the emergency) or as a regulatory requirement (e.g., for SAEs or death). Note that there is no specific antidote or method of removing the study drug from the body (such as dialysis) and the best available care for the patient should be continued.

If the blind is broken, the date, time and reason must be recorded in the patient's e-CRF and any associated AE report. It is the responsibility of the investigator to promptly document and explain any unblinding to the sponsor/CRO.

Detailed instructions for the use of the IWRS in order to break the study blind for a patient are provided in a separate document that will be filed in the Site File and Trial Master File. As well as the IWRS, a backup system enabling unblinding of treatment is provided to the sites.

After a patient has been unblinded data collection should continue as per protocol.

Suspected unexpected serious adverse reactions (SUSARs), which are subject to expedited reporting, should be unblinded by the Pharmacovigilance group before submission to the regulatory authorities and IECs/IRBs (Independent Ethics Committee/Institutional Review Boards).

The overall randomisation code will be opened only for reporting purposes. This will occur when all D28 clinical data have been entered into the database and all data queries related to D28 have been resolved, and the assignment of patients to the analysis sets and database lock has been completed. After completion of the extended follow up of 90 days and resolving related queries the database is locked again for D90 analyses.

#### **5.5 Drug Accountability**

The Investigator is responsible for maintenance of accurate study drug accountability records throughout the study.

Each dispensing of study drug will be documented.

The Investigator is responsible for ensuring all unused medication is destroyed at the investigational site following the appropriate drug accountability procedures.

## 5.6 Compliance

The study drugs are administered intravenously at the study site, so it is not necessary to monitor patient compliance with the study drug regimen.

## 5.7 Previous and Concomitant Medications

Any medication the patient takes other than the study drug between screening and D28, including herbal and other non-traditional remedies, is considered to be a concomitant medication. All concomitant medications (for previous 7 days) must be recorded in the e-CRF except for nutritional and volume therapy, electrolyte support, vitamins and supportive therapies such as artificial tears, ointments, etc. The following information must be recorded in the e-CRF for each concomitant medication: generic name, route of administration, start date, stop date, dosage and indication. Any changes in the dosage or regimen of a concomitant medication must be recorded in the e-CRF. If a patient is discharged from the hospital prior to D28 then the patient must be instructed that the Investigator should be informed about additional medication up to D28.

Concomitant medications or therapies that are considered necessary for the patient's welfare and that will not interfere with the study drug may be given at the discretion of the attending physician.

All patients in this study will be managed with supportive care measures according to the best practice established locally in study centre and in accordance with the treatment guidelines (<https://www.covid19treatmentguidelines.nih.gov/therapeutic-management>).

There are no prohibited co-medications in this study, except for systemic corticosteroids, baricitinib and tofacitinib (and other JAK-STAT signalling pathway inhibitors) as these agents have been demonstrated to have potential inhibitory effect on IFN beta.

# 6 STUDY CONDUCT AND ASSESSMENTS

## 6.1 General Considerations

The study will utilize standard clinical care laboratory assessments for safety, in order to avoid excessive sampling of blood in hospitalized subjects. Complete Blood Count (CBC), White Blood Cells (WBC) differential and biochemistry, for example, will be collected from clinical routine if available; if not then these will be collected as protocol specific assessments from pre-dose D1, D2-D7, D10, D14, D28/last day in hospital. The timing of the assessments is shown in the [Table 2](#) Schedule of Procedures (below). Laboratory assessments needed for CBC, differential and chemistry should be taken on the timepoints indicated in the [Table 2](#), if not available by clinical standard of care (i.e., analyses should not be duplicated if available by clinical routine).

For the purposes of this study, study day 1 (D1) is defined as the first calendar day (from midnight to the following midnight) of treatment with IFN beta-1a or dexamethasone. All days thereafter are defined as "Dn" (e.g., D2, D3, etc.) until D28.

Baseline assessments are defined as those assessments carried out in the screening period and pre-dose D1 (before the first dose of study drug on D1). Unless withdrawn from study or discharged from the hospital, all patients will receive study drug for 6 consecutive days (D1-D6). All assessments in the period up to D28 are only to be performed when a patient is in hospital. Study assessment at D14, D28 and D90 are performed by phone call if the patient is not any longer present at the hospital, or sought through records if the patient cannot be contacted. The end of the study will be the date of last patient/last visit at D90.

**Table 2. Schedule of procedures and assessments**

Procedure	Screening	D1 pre-dose	D1-D6	D7-D14 	D15-D27	D28 short-term follow-up 	D90 long-term follow-up (+/- 7 days)
Informed consent	X						
Inclusion/exclusion criteria	X	X					
Demographics	X						
Medical history	X						
Physical examination (incl. weight and height at screening)	X					X	
Pregnancy test in women of childbearing potential	X						
Review and documentation of available lung X-ray / CT scan	X						
Genetic sample		X 					
Randomization		X					
Administration of study drug			X				
Specimen collection  :							
MxA		X	X	X			
CD73		X	X	X			
PIMs 		X	X	X			
IFN beta		X	X	X			
ADAs		X				X	
COVID-19 test (if positive result of a test taken within the last 7 days is not available)	X						
COVID-19 for viral load PCR 		X	X	X			
Nasopharyngeal swab for virus variant analysis		X					
Biochemistry, CBC & Differential 		X	X	X		X	
Data collection from medical records:	X	X	X	X		X	X
WHO 9-point ordinal scale		X	X 	X 		X 	
Previous and concomitant medications and interventional therapies	X	X	X 	X 	X 	X 	
Clinical status assessments 		X	X	X	X	X	X
Vital signs 		X	X	X	X	X	
Adverse events 	X	X	X 	X 	X 	X 	X

*All daily assessments should be obtained at the same time as D1 pre-dose assessment (+/- 2 hours). The specimen collections and assessments at pre-dose D1 should be within 4 hours prior to the administration of study drug.*

1. *If the subject is not in the hospital, information to be collected by phone on D14 and D28*
2. *Short term follow-up; D28 or Day of discharge from hospital (whichever is earlier).*
3. *Blood collection for MxA, CD73 and PIMs will occur: pre-dose on D1, D3, D5; and on D7 for hospitalized patients (for IFN blood collection will occur: pre-dose D1, D1(5 minutes after D1 dosing), pre-dose on D3 and on D7). Blood collection for ADA will occur: pre-dose D1 and D28 or Day of discharge from hospital (whichever is earlier).*
4. *PIM = Potential Inflammatory and interferon signalling Markers on a protein and RNA level (Nanostring); DNA for genetic analyses will be extracted from the pre-dose PIM sample*
5. *A blood sample for PCR copy number quantification (SARS-CoV-2 test) will be collected on pre-dose D1 and on D3, D7, D10 and D14 (if subject's discharge is before D14, the specimen is obtained also on the day of discharge).*
6. *Biochemistry, CBC & Differential; Complete blood count & WBC differential (defined in Table 3) to be collected as performed locally and part of standard of care (pre-dose D1, D2-D7, D10, D14, D28/last day in hospital)*
7. *Includes the following assessments: Survival, hospital status, ICU status, renal support, ECMO, oxygen support, and mechanical ventilation. Assessments for D14 and D28 by phone for non-hospitalized subjects. Survival to be addressed from health records if patient cannot be contacted by phone (for D90 only survival and hospital status will be collected)*
8. *Vital signs pre-dose, 30 and 60 minutes (+/-10 minutes) after study drug administration (D1-D6), D7-D28 daily until discharge from hospital*
9. *Information collected by phone for non-hospitalized subjects. Survival to be addressed from health records if patient cannot be contacted by phone.*

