### 2.3.4 Clinical safety experience of IV IFN beta-1a

In all of the above-mentioned trials, the use of IFN beta-1a has not been associated with significantly increased risks or adverse events in comparison to placebo. Fever was the most common adverse event in both phase III trials.

In the INTEREST trial, 18 (12.5%) study subjects and 12 (7.9%) study subjects in the IFN beta-1a group and placebo groups, experienced fever as an AE. Anaemia was the second most common AE (16 [11.1%] study subjects and 11 [7.2%] study subjects in the IFN beta-1a group and placebo groups, respectively).

In the Japanese phase III trial (MR11A8-2) fever was reported more frequently (34.7% and 6.8%) as an AE for IFN beta-1a and placebo groups, respectively. The second most commonly reported AE was decreased platelet count (6.1%) in the IFN beta-1a group and increased hepatic enzymes (6.8% in both groups).

The incidence of serious adverse events (SAEs) in the INTEREST trial (fatal and non-fatal) was similar in the active (53.5%) and placebo (50.7%) groups. The overall incidence of AEs considered related to study drug was higher in the active group (28.5%) compared with the placebo group (21.7%).

The incidence of SAEs in the MR11A8-2 trial (fatal and non-fatal) was similar in the active (53.1%) and placebo (47.7%) groups, but none of the events were strongly suspected of being causally related to the study drug.

In healthy volunteers IV IFN beta-1a induced a decrease in circulating neutrophils below lower limit of normal approximately three days after the first dose. Blood neutrophils returned to normal range within a few days after the last administered dose. One possible explanatory mechanism is that IFN causes the transfer of neutrophiles from the blood to the tissue ("marginalization) as a precaution to IFN signal and against the possibility of viral presence. In severely ill patients in clinical studies FPCLI002 and MR11A8-2 a similar phenomenon was not observed (Clinical study FP1CLI011, Faron data on file).

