Phase III clinical studies (INTEREST and MR11A8-2) and phase I clinical study (FP1CLI011) in healthy volunteers did not identify any major safety risks for FP-1201-lyo. A decrease in IL-6 IL-8 and IFN-gamma values was observed in patients treated with FP-1201-lyo, a finding that was similar to those found in a placebo group (Ranieri et al. 2020). Fever was the most common AE in phase III studies, and all healthy volunteers in the study FP1CLI011 experienced fever as a response to the treatment. The pyrogenic effect is characteristic for IFN beta-1a as well as for other type I IFNs. In healthy volunteers, the body temperature characteristically reached 38–39°C (axillary) 1-2 hours after the FP-1201-lyo administration, and this elevation persisted for around 2 hours (all treated with antipyretic analgesics). The temperature elevations vary substantially among individuals. IFN beta-1a induced fever responds to antipyretic analgesic drugs, which are recommended to decrease (or prevent) the flu-like symptoms associated with IFN beta-1a administration. Serious adverse reactions possibly related to IFN beta-1a reported more than once in phase III clinical trials, include two cases of increased transaminases, two cases of thrombocytopenia, three cases of hypertension, and two cases of rhabdomyolysis. The available information suggests that the present study's risk/benefit ratio is favourable.

Investigating the effect of IFN beta-1a to prevent ARDS in viral pneumonia (and particularly SARS-CoV-2) is especially intriguing because of the potential beneficial effects of IFN beta-1a in direct viral defense, association of type I IFN deficiency with worse outcomes in COVID-19 (Hadjadj et al 2020, Zhang et al. 2020), and the induction of CD73-mediated preventive effects on endothelial barrier function and pulmonary capillary leak. The current study aims to detect the benefit of IFN beta-1a in clinical outcome measures (WHO 9-point ordinal scale), reduced need of mechanical ventilation, mortality and development of organ failure and ARDS versus the current standard of care for COVID-19. Dexamethasone was chosen as the comparator arm to align with treatment guidelines for hospitalized COVID-19 patients requiring supplemental oxygen. The rationale underlying the current design is provided below. Safety of both treatment arms will be assessed equally.

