### 6.3 Study Assessments During Hospital stay

The following in-hospital data will be collected to assess trial efficacy and safety endpoints. Most data may be assessed by medical record review.

1. Administration of study drug once daily for 6 days
2. Close monitoring of vital signs for the 60 minutes following study drug administration
3. Specimen collection including COVID-19 sample per [Table 2](#).
4. WHO 9-point ordinal scale
5. Concomitant medications and therapies
6. Clinical status assessments
7. Adverse events
8. Hospital discharge disposition.

The specimen collection should be prior to the administration of study drug and within +/-2 hours of the sampling time at D1.

If a subject has been discharged from the hospital but is re-admitted before Day 28 to the study site for COVID-19 associated reasons, the data for the visits assessments are recorded in CRF. Laboratory samples are not taken from re-admitted subjects, but, if possible, a serum sample for determining the viral load should be taken according to the timepoints in [Table 2](#). The re-admission to hospital is reported as a SAE.

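### On dosing days the planned temperature readings stop at 60 minutes, the earliest edge of the fever interval that the protocol itself describes for IFN beta-1a

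*Protocol*

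**What the plan says.** **Schedule.** Footnote 8 to Table 2 of the protocol reads "Vital signs pre-dose, 30 and 60 minutes (+/-10 minutes) after study drug administration (D1-D6"), followed by one reading a day from D7 to D28 while the patient is in hospital. Section 6.3 repeats the limit: "Close monitoring of vital signs for the 60 minutes following study drug administration". The general note under Table 2 ties daily assessments to the clock time of the D1 pre-dose assessment, within 2 hours either way, so no later reading is planned on the same day. Section 6.3.1 lists temperature among the vital signs.

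**Expected reaction.** Section 2.6 says that temperature in healthy volunteers characteristically reached 38-39°C (axillary) "1-2 hours after the FP-1201-lyo administration, and this elevation persisted for around 2 hours (all treated with antipyretic analgesics"). It adds: "The temperature elevations vary substantially among individuals". It also reports that every volunteer in FP1CLI011 had fever. Section 2.3.4 states: "Fever was the most common adverse event in both phase III trials".

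**Role in the trial.** Safety and tolerability against dexamethasone is a primary objective (section 3.1), and vital signs are a safety criterion (section 4.2.1). The synopsis describes the vital signs used for safety as coming from routine care.

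**The concern.** The schedule and the background section do not fit together. The protocol says when its best-known drug reaction should appear, then ends the timed readings as that period begins. The 30-minute reading comes before it, the 60-minute reading sits on its boundary, and the next planned reading comes long after it.

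Timed temperature is the one objective measure of this reaction that would be taken in the same way at every site and in both arms. Without it, the size and timing of the temperature rise under each treatment rest on what staff happen to record or report. That matters more here than in volunteers, because fever is also a symptom of COVID-19 and one of the two drugs is a corticosteroid.

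**Working it through.** The plan gives no figure to reproduce. The check compares two time windows and then sizes the overlap.

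**Inputs**
- Post-dose readings at 30 and 60 minutes, each ±10 minutes (Table 2, footnote 8): 20-40 and 50-70 minutes.
- 38-39°C reached at 60-120 minutes (section 2.6).
- Elevation lasting about 120 minutes (section 2.6).
- Next planned reading: the next day, at the D1 pre-dose clock time ±2 hours. The D1 pre-dose assessment may be up to 4 hours before dosing (note under Table 2).

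**Step 1: febrile interval.** The earliest start is 60 minutes. The latest end is 120 + 120 = 240 minutes. The interval is 240 − 60 = 180 minutes long.

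**Step 2: overlap with the planned readings**
- 30-minute reading (20-40): none.
- 60-minute reading (50-70): at most 70 − 60 = 10 minutes, and 10/180 = 5.6% of the interval.
- Next-day reading after the D1 dose: no earlier than 24 − 4 − 2 = 18 hours after dosing, against an interval that ends at about 4 hours.

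**Step 3: share of fevers already at 38-39°C at the last reading.** The protocol gives only the range 1-2 hours, so a distribution has to be assumed. Two forms were used:
- Uniform over 60-120 minutes: F(t) = (t − 60)/60. So F(60) = 0 and F(70) = 10/60 = 16.7%. Averaged over a reading time spread evenly from 50 to 70 minutes: (1/20) × 10²/(2 × 60) = 4.2%.
- Normal, centred on the midpoint of 90 minutes: F(t) = Φ((t − 90)/SD), with SD 15, 20 or 30 minutes.

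| Assumed time to 38-39°C | At 60 min | At 70 min | Averaged over 50-70 min |
|---|---|---|---|
| Uniform, 60-120 min | 0% | 16.7% | 4.2% |
| Normal, SD 15 | 2.3% | 9.1% | 3.1% |
| Normal, SD 20 | 6.7% | 15.9% | 7.5% |
| Normal, SD 30 | 15.9% | 25.2% | 16.3% |

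The SD 30 row is generous to the schedule, since it puts 2 × 15.9% = 31.8% of times outside the 1-2 hours that the protocol states. Even so, about 75% of fevers have not been reached at the latest permitted reading.

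**Step 4: where the interval is best covered.** On the protocol's own range, everyone who reacts has reached 38-39°C by 120 minutes, and the earliest fever ends at 60 + 120 = 180 minutes. Only between 120 and 180 minutes would all of them be febrile together.

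**The case against.** The strongest reply is that fever does not depend on timed readings to be found, and much of that stands.

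- **Adverse events.** Section 6.6.1.1 collects them by observation, spontaneous report and open questioning, with no 60-minute limit. Section 6.6.1.3.4 allows abnormal vital signs to be adverse events. Section 6.6.1.3 does let common aberrations in these patients go unrecorded, but it makes an exception for those that need intervention. Section 2.6 recommends antipyretics for this fever, so a treated fever would arguably meet the exception. Section 5.7 records concomitant medication with its indication.
- **Routine readings.** The synopsis says that routine clinical assessments will be used for safety and efficacy, and section 6.3 allows most data to come from the medical record. Ward temperatures may therefore exist, although at unplanned times. Section 7.2.1.3 lists but does not summarise extra vital signs from non-protocol visits or adverse event work-up. Whether it covers routine ward readings is unclear.
- **Source of the timing.** It comes from healthy volunteers who all received antipyretics, measured at the axilla, with substantial variation. No timing is given for COVID-19 patients. The 1-2 hours is when 38-39°C was reached, so a reading at 60 minutes may already show a rise.

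Three stronger inferences are tempting, and the documents do not support them.

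1. *The primary tolerability comparison is biased toward no difference.* Section 7.6 specifies antibody counts and adverse event summaries and no between-arm temperature analysis. Adverse event reporting did show fever differences in the earlier phase III trials: 12.5% against 7.9%, and 34.7% against 6.8% (section 2.3.4).
2. *Nearly every interferon dose would have a missed fever.* Multiplying 70 patients by 6 doses gives 420 administrations, but that assumes fever at every dose. In the phase III patients fever was reported as an adverse event in 12.5% and 34.7%, and section 5.3 ends dosing at discharge.
3. *The 30-minute reading is wasted and can be moved.* It falls within the close monitoring that section 6.3 calls for, and nothing in the documents shows that it is dispensable.

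The reply leaves one thing unanswered: no planned temperature falls inside the interval apart from its first minutes. Uncertainty about timing in patients is a reason to read later than the earliest edge.

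**Conclusion.** The mismatch is real and internal to the protocol. The planned readings overlap at most 10 of about 180 minutes of the fever interval. Under the assumed distributions, about 0-16% of fevers would be reached by the nominal 60-minute reading and about 9-25% by the 70-minute limit. The schedule largely misses the reaction but not entirely, and the figures rest on volunteer timing carried over to patients and on distributions that the protocol does not give.

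The gap is confined to timed, objective temperature data. It is not a failure of all fever capture, and it does not show bias in a primary comparison.

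For the final report the effect is small. The SAP (sections 2, 6 and 9) records termination with five patients dosed, sets no hypothesis tests and plans vital signs only as Listing 21, with no summary table. At most 5 × 6 = 30 dosing occasions are involved, across both arms. This is a minor point: a cheap improvement for any future use of the design, and a caution when reading that listing.

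**What to change.** Reconcile footnote 8 of Table 2 and section 6.3 with section 2.6, so that at least one planned post-dose set of vital signs, including temperature, falls within the interval that the protocol gives for the reaction. Keep the 30- and 60-minute readings. The exact time is for the sponsor to choose; step 4 above shows which part of the interval covers most of it. The change concerns when temperature is measured, not how fever is treated.

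In the analysis plan, present maximum post-dose temperature descriptively by arm and dose day, and say whether routine ward readings count toward it or come under section 7.2.1.3.

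The cost is one extra bedside reading per dose, at most six per patient, in people who are already inpatients. For the trial as it ended, a sentence beside Listing 21 is enough: the timed readings stop at 60 (±10) minutes, so normal values there say little about fever later the same day.
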